## 7 Safety and Adverse Events

The definitions below are included in the protocol as part of the template provided by the NYU School of Medicine IRB.

#### Serious Adverse Event

Adverse events are classified as serious or non-serious. A **serious adverse event** is any AE that is:

- fatal
- life-threatening
- requires or prolongs hospital stay
- results in persistent or significant disability or incapacity
- an important medical event

All adverse events that do not meet any of the criteria for serious should be regarded as **non-serious adverse events**.

#### Severity of Event

For AEs not included in the protocol defined grading system, the following guidelines will be used to describe severity.

- **Mild** – Events require minimal or no treatment and do not interfere with the participant's daily activities.
- **Moderate** – Events result in a low level of inconvenience or concern with the therapeutic measures. Moderate events may cause some interference with functioning.
- **Severe** – Events interrupt a participant's usual daily activity and may require systemic drug therapy or other treatment. Severe events are usually potentially life-threatening or incapacitating.

### 7.1.2 Relationship to Study Intervention

*All AEs will have their relationship to study intervention or study participation assessed with a level of specificity appropriate to the study design.*

- **Related** – *The AE is known to occur with the study intervention, there is a reasonable possibility that the study intervention caused the AE, or there is a temporal relationship between the study intervention and event. Reasonable possibility means that there is evidence to suggest a causal relationship between the study intervention and the AE.*
- **Not Related** – *There is not a reasonable possibility that the administration of the study intervention caused the event, there is no temporal relationship between the study intervention and event onset, or an alternate etiology has been established.*

### 7.2 Time Period and Frequency for Event Assessment and Follow-Up

The occurrence of an AE or SAE may come to the attention of study personnel during study visits and interviews of a study participant. All AEs including local and systemic reactions not meeting the criteria for SAEs will be captured on the appropriate RF. Information to be collected includes event description, time of onset, staff's assessment of severity, relationship to study intervention (assessed only by those with the training and authority), and time of resolution/stabilization of the event. All AEs occurring while on study must be documented appropriately regardless of relationship. All AEs will be followed to adequate resolution.

The PI will record all reportable events with start dates occurring any time after informed consent is obtained until 7 (for non-serious AEs) or 30 days (for SAEs) after the last day of study participation. At each study visit, the investigator will inquire about the occurrence of AE/SAEs since the last visit. Events will be followed for outcome information until resolution or stabilization.

All unresolved adverse events should be followed by the investigator until the events are resolved, the subject is lost to follow-up, or the adverse event is otherwise explained. At the last scheduled visit, the investigator should instruct each subject to report any subsequent event(s) that the subject, or the subject's personal physician, believes might reasonably be related to participation in this study. The investigator should notify the study sponsor of any death or adverse event occurring at any time after a subject has discontinued or terminated study participation that may reasonably be related to this study.

### **7.2.1 Event Reporting**

The Investigators will be responsible for recording and reporting adverse events and unanticipated problems, as defined by the NYU School of Medicine IRB. The Investigators will ensure that they are knowledgeable of the definitions for safety and adverse events. All adverse events occurring during the course of the study will be recorded. The current study includes surveys and interviews, and does not involve diagnostic procedures or clinical treatment. Should an adverse event occur, the event will be recorded and followed until resolution, stabilization or until it has been determined that participation in the study was not the cause of the adverse event. Serious adverse events that are ongoing at the end of the study will be followed up to determine the final outcome. All serious and unexpected adverse events (e.g., hospitalizations, life threatening events, death) or other unanticipated problems that involve risk to study participants or others and whether these appeared related to the research assessment protocols will be reported to the NYU School of Medicine IRB, the Uganda's National Science and Technology IRB, and the Chair of the DSMB. The DSMB has the authority to halt the preventive trial if it perceives that harm is occurring due to the program. Summaries of adverse events reports will be also made to Clinicaltrials.gov bi-annual update/report and NIH in the yearly progress report, unless the nature of a particular event is such that it bears reporting to NIH immediately.

### **7.3 Safety Oversight**

**DSMB:** An independent group of experts that advises the study investigators. The primary responsibilities of the DSMB are to 1) periodically review and evaluate the accumulated study data for participant safety, study conduct and progress, and, when appropriate, efficacy, and 2) make recommendations concerning the continuation, modification, or termination of the trial.

We shall include the following:

- An expert in the conduct of preventive trials and all phases of intervention research (i.e., [name])
- Two professionals with substantive expertise in the area of child health promotion (i.e., two Ph.D. level researchers: [name] from the US and [name] from Uganda).
- A biostatistician with expertise in prevention trials (i.e., [name])
- The DSMB will perform the following activities:
  - Review the research protocol and plans for data and safety monitoring.

- Evaluate the progress of the prevention program implementation, including periodic assessments of data quality and timeliness, participant recruitment, accrual and retention, participant risk versus benefit, performance of trial sites, and other factors that can affect study outcome.
- Monitors will also consider factors external to the study when interpreting the data, such as scientific or behavioral problem development that may have an impact on the safety of the participants or the ethics of the study.
- Make recommendations to the IRB and investigators concerning continuation or conclusion of the trial(s).
- Protect the confidentiality of the trial data and the results of monitoring.

The DSMB will meet with PI [name], subcontract-PI [name] and the sub-Investigators yearly to review adverse events reports and dropout rates. Data will be provided at those meetings by the investigators on key variables that may indicate harm. The DSMB biostatistician will evaluate confidentiality and integrity of the database, and the procedures for recording and storing confidential files. The DSMB will also review the elements of the plan to deal with emergencies.

## 8 Clinical Monitoring

In the event of a clinical emergency or other crisis, research staff and trainer/implementers (MHPs & TTC faculty) will be trained in basic crisis management. Staff will be trained in a manualized protocol for handling a variety of crises that may be presented to staff at the schools. The protocol for handling these issues addresses the safety of both study participants and study staff. The protocol also details the need for supervision in all instances. They will also notify Ugandan PI and Co-I (clinicians and researchers) or contact them by mobile phone if needed. Ugandan PI and the Clinical Research Director will oversee our program for the study schools and children. If medical attention or follow-up is needed, they will refer them to local Hospital or other health agencies. If additional medical consultation is needed regarding the adverse event, we will consult with the needed specialists or consulting services.

[figure not shown]
Research staff will also be available to talk individually with any participant who becomes distressed during program participation, and referrals will be made for participants as needed (e.g., teachers who expresses concern about their students' well-being).>

## 9 Statistical Considerations

**Data Analysis Plan for Aim 1.** Prior to any outcome analyses, we will generate summary statistics for all data, summarizing with means and standard deviations for continuous variables and frequencies for categorical variables. The distribution of study variables and missing data patterns will be inspected. To estimate effectiveness, we will apply intention-to-treat (ITT) analyses and first focus on between-subject comparisons of intervention vs. control (comparing *PD* to control, comparing *PDT* to control, and comparing *PD* to *PDT*). We will estimate the impact of *PD* on children and teachers post-intervention (T2, 4-5 months after T1) and at one-year follow up (T3, 18 months after T1, or 12 months after T2). **Figure 4** below describe the model to be tested under Aim 1. School and class nesting will be considered, and a multiple imputation strategy will be applied to account for missing data. Linear mixed effect models, using SAS PROC MIXED, will be applied to examine short and longer-term impacts. We will first examine the immediate impact by modeling post-intervention outcomes (T2) as a function of intervention, adjusting for T1 outcome measures. The model accounts for between-subject (within-school and -class) correlation by including school- and classroom-level (when appropriate) random intercepts. The outcomes will be modeled as:  $Y_{ij} = \beta_1 I_j + \beta_2 C + \beta_3 X_{ij} + \gamma_j + \gamma_k + \epsilon_{ijk}$ , where  $Y_{ij}$  is the outcome for the student  $i$  in school  $j$ .  $I_j$  is intervention status (a categorical variable, with 3 levels) for school  $j$ , representing two dummy variables (control as the reference).  $C$  is the cohort indicator for

school, where  $C=1$  if is in the second cohort, 0 for the 1st cohort.  $X_{ij}$  is the baseline value of the outcome for student  $i$  in school  $j$ . In the models,  $\beta_1$  represents the intervention impact,  $\beta_2$  is the effect of the second cohort,  $\beta_3$  is the effect of baseline measure,  $\gamma_j$  is the school-level random effect and  $\gamma_k$  is the class-level random effect (when appropriate), and  $\epsilon_{ijk}$  is the error term for student  $i$  in school  $j$  and  $k$  class. Next, we will study longer-term effectiveness outcomes (T2 to T3) by applying growth curve models and using repeated assessments over time. In these growth models, we will add time-relevant parameters to the model above, including school-level random slopes. The post-baseline scores will be modeled as a linear function of time/slopes, intervention indicator, and intervention-by-time interactions, adjusting for T1 scores and cohort. The long-term outcome will be modeled as:  $Y_{ij} = \beta_1 I_j + \beta_2 t + \beta_3 I_j * t + \beta_4 C + \beta_5 X_{ij} + \gamma_j + \gamma_k + \epsilon_{ijk}$ . A significant  $\beta_3$  would indicate the effect of the intervention depends on time; in this case, we will estimate the slopes for each condition, and the difference between the conditions with respect to the mean outcome scores. The analytical methods that we propose have been applied successfully in our previous US and LMIC studies. Cost-effectiveness analysis of *PD* and *PDT* implementation models will be examined using approaches that have been applied in previous school-based and parenting-based child mental health promotion research. The analysis will center on incremental cost-effectiveness ratios (ICERs), where the numerator represents the cost difference between the intervention arms and the control, and the denominator represents the difference in average intervention effects. To that end, the cost-effectiveness analysis of the intervention will involve examining how much the *PD/PDT* intervention costs to achieve a unit of effect relative to the control group. The effects of the intervention will be estimated using the effect sizes  $d$  (standardized mean difference between comparison groups) from an ITT approach. For the effectiveness outcomes, we will use an effect size of 0.2-0.4 as a benchmark; this corresponds to a small to medium effect size according to Cohen. We will calculate the ICERs and compute the per-participant cost per 0.2-0.4 SD change for each effectiveness outcome. Reporting of the analysis will follow the Consolidated Health Economic Evaluation Reporting Standards (CHEERS).

[figure not shown]

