Phase	Phase II/III
Objectives	This study include three specific aims: Aim 1. To evaluate the short- and longer-term effectiveness of, PD alone ( PD ), PD + T-Wellness ( PDT ), and control (C, provision of child mental health and referral information). Hypotheses: (a) PD is more effective than control; and (b) PD with T-Wellness ( PDT ) is more effective for CHWs/teachers than PD alone; and (c) PDT has a more favorable cost-effectiveness ratio than PD alone; Aim 2. To examine effectiveness mechanisms and theory of change underlying the EBIs. Hypotheses: the mediational mechanisms of PD (teacher EBI strategy use as a mediator between intervention and child outcomes) and PDT (teacher stress management and EBI strategy use as mediators) will be supported; Aim 3. To examine implementation contextual factors and mechanisms that contribute to CHWs' (teachers') uptake and sustainment of EBI strategies within PD and PDT schools. Hypotheses: better fidelity, teacher mental health and more supportive contexts will be associated with better teacher uptake and sustainment of EBI strategies and more effective task-shifting.

Methodology	A cluster randomized controlled trial (cRCT), single blind and mixed-methods design will be applied. All study activities will be conducted in Uganda. Thirty-six public primary schools (18 urban and 18 rural), 540 teachers (~15 per school) and 1,980 parent-child pairs (~55 per school) will be recruited. Schools will be assigned to one of three conditions (PD, PDT, control). A stratified-block randomization procedure will be applied to ensure approximately similar characteristics across study regions and conditions.
Endpoint	Effectiveness outcomes will be assess 3 times (Time 1= before intervention; Time 2= immediate after PD/PDT intervention; Time 3= 12 months after Time 2). The primary teacher effectiveness outcomes (or intermediate effectiveness outcomes) are teachers' EBI strategy use and teacher stress management. The primary child effectiveness outcomes are child externalizing and internalizing problems (mental health outcomes). The secondary child effectiveness outcomes are emotion regulation, executive functioning (ability for cognitive processes that are foundation for the cognitive control of behavior), and social relationship (student-teacher relationship, peer relationship).

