Description of Study Intervention/Procedure	

• Prior to the RCT study (or during Year 1), T-Wellness Package (a brief teacher stress management psychoeducation package, adapted from EBIs and including a half-day workshop for common stress management and a half-day for burnout management, and three follow-up group support sessions) will be tested to insure user-centeredness. we will recruit 4 study schools and applying factorial design to test the effect of each component (1 Common Stress management; 1 Burnout Stress management; 1 Combined Common and Burnout Stress management; 1 control; with ~15 teachers in each condition). Both groups' will also receive 3 post-workshop group support sessions. We will compare pre-post differences on teacher stress management and mental health using a mixed-methods data collection.

• To implement PD/PDT using a scalable approach, we will formalize partnership with the Ugandan Ministry of Education (MOE), Ministry of Health (MOH), academic medical center, and Teacher Training Colleges (TTCs) stakeholders in Year 1. The partnership and intervention implementation team will receive training from NYU PD trainers, and implement PD/PDT in Years 2-4.

• To study effectiveness-implementation aims (Aim 1-3), a cRCT will be conducted. Public primary schools from Kampala/urban and Hoima/ rural will be recruited. A stratified-block randomization procedure will be applied to ensure approximately similar characteristics across geographic regions and three intervention conditions (PD, PDT, and control). Teachers from the PD will receive a 3-day training, and teachers from the PDT will receive a 4-day training. Both intervention groups will receive 8 group-coaching sessions (with teachers from their own school). Teachers from the control schools will receive child mental health promotion materials. They will receive T-Wellness in Year 4 after the evaluation study is completed. Given the large numbers of students in schools, research staff will randomly select 10% of students and families from each school for participation in the evaluation study. A total of 1,980 families (parent-child pairs) from 36 schools (averaging 55 families/per school) will participate in the evaluation study. Effectiveness outcomes will be assessed at 3 time points over 18 months (baseline/T1, post-PD or PDT, 5-6 month/T2, and 16-18-month follow-up/T3). Objective observation, implementers, school staff, parent, and child report data (quantitative and qualitative) will be gathered.

• To study underlying mechanisms, we will use the evaluation data describe above to examine whether intervention effects on children's mental health outcomes is mediated through improvement on teachers' EBI practices (primary) and teacher stress coping. To study moderation mechanisms, geographic region, fidelity (including adherence, quality of program implementation, engagement, exposure) and other implementation contextual factors (i.e., EBI fidelity, school climate), guided by the Consolidated Framework for Implementation Research, will be studied.

• Identifiers will be removed from the identifiable survey and field notes. Data may be used for future research studies or shared with other researchers and we will not request additional informed consent from you to use these specimens as we have noted here.

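### Randomisation is meant to balance regions, but the Aim 1 models carry no region term: if region predicts outcome after T1 score and cohort, the T2 and T3 arm contrasts lose power

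*Combined protocol and SAP*

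**What the plan says.** **Design.** The Methodology entry of the Protocol Summary gives the sample: "Thirty-six public primary schools (18 urban and 18 rural), 540 teachers (~15 per school) and 1,980 parent-child pairs (~55 per school"). On allocation it says: "A stratified-block randomization procedure will be applied to ensure approximately similar characteristics across study regions and conditions". The intervention description in the same summary repeats this: "A stratified-block randomization procedure will be applied to ensure approximately similar characteristics across geographic regions and three intervention conditions". Section 4.4 (Schools) also names urban/rural location among the factors on which a statistician matches schools, beside size and performance.

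**Analysis.** Section 9 takes as the Aim 1 impact estimates the effects on "children and teachers post-intervention (T2, 4-5 months after T1) and at one-year follow up (T3, 18 months after T1"). The T2 analysis is described as "modeling post-intervention outcomes (T2) as a function of intervention, adjusting for T1 outcome measures". Its equation has arm, cohort, the T1 score and school and class random effects. In the longer-term model, post-baseline scores are "modeled as a linear function of time/slopes, intervention indicator, and intervention-by-time interactions, adjusting for T1 scores and cohort". Neither equation has a region term.

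**Where region does appear.** Table 2 lists it as the primary moderator. Aim 3 then adds moderator and interaction terms in separate models.

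**The concern.** Balancing a factor across arms removes its variation from the true sampling error of an arm contrast. A model that omits the factor puts that variation back into the school random effect, so the reported standard error is larger than the real one. The design pays for the balance and the analysis gives the gain away.

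Each contrast compares 12 schools with 12, so between-school variance matters. What is at stake is power for the T2 and T3 arm differences, for child and teacher outcomes. Estimates stay unbiased and the type I error falls below nominal rather than rising above it.

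**Working it through.** The plan states no power, alpha, ICC or detectable effect, so there is no figure of its own to reproduce. The counts agree: 36 × 55 = 1,980 and 36 × 15 = 540.

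**Inputs from the documents.** 36 schools, 12 per arm, 18 urban and 18 rural (6 per arm per region if balanced); 55 children and 15 teachers per school; 18 schools per cohort (data-collection rows of Table 1). The effect range comes from the cost-effectiveness text: "we will use an effect size of 0.2-0.4 as a benchmark".

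**Assumptions.** Two-sided 5%; residual variance 1 after T1 score and cohort; ICC 0.05 (range 0.02 to 0.10) on that scale, region included; region crossed with cohort. The gap g is the urban-rural difference in residual SD, so region variance is g²/4. The effect is also in residual SD.

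**Step 1: standard error with no gap.** The variance of a school mean is v = ICC + (1 − ICC)/m, and SE = √(2v/12).
- Child: v = 0.05 + 0.95/55 = 0.0673; SE = 0.1059; between-school share 0.05/0.0673 = 74%.
- Teacher: v = 0.05 + 0.95/15 = 0.1133; SE = 0.1374; share 44%.

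**Step 2: effect of a gap (child).** The true variance of a school mean, for the contrast, is v − g²/4. Without region, the residual mean square on 32 df has expectation (v − g²/4) + 36(g²/4)/32.
- g = 0.14: true 0.0673 − 0.0049 = 0.0624, SE 0.1020; model 0.0624 + 0.0055 = 0.0679, SE 0.1064.
- g = 0.24: true 0.0673 − 0.0144 = 0.0529, SE 0.0939; model 0.0529 + 0.0162 = 0.0691, SE 0.1073.

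Simulation of 36 school means (100,000 replicates) agrees. Mean model SE against empirical SD is 0.1055 against 0.1021 at g = 0.14 (3% too wide) and 0.1065 against 0.0940 at g = 0.24 (13% too wide). Type I error without region is 4.9%, 4.2% and 2.6% at gaps 0, 0.14 and 0.24. With region it is 4.9%, 5.1% and 5.0%.

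**Step 3: power without and with region.**

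| Outcome | ICC | Effect | Gap | Without | With |
|---|---|---|---|---|---|
| Child T2 | 0.05 | 0.3 | 0 | 78% | 78% |
| Child T2 | 0.05 | 0.3 | 0.10 | 79% | 80% |
| Child T2 | 0.05 | 0.3 | 0.14 | 79% | 81% |
| Child T2 | 0.05 | 0.3 | 0.24 | 80% | 87% |
| Child T2 | 0.05 | 0.2 | 0.24 | 43% | 54% |
| Child T2 | 0.05 | 0.4 | 0.24 | 97% | 98% |
| Child T2 | 0.02 | 0.3 | 0.24 | 98.1% | 99.7% |
| Child T2 | 0.10 | 0.3 | 0.24 | 55% | 61% |
| Teacher T2 | 0.05 | 0.3 | 0.14 | 56% | 58% |
| Teacher T2 | 0.05 | 0.3 | 0.24 | 56% | 62% |
| Child T3 level | 0.05 | 0.3 | 0.14 | 68% | 70% |
| Child T3 level | 0.05 | 0.3 | 0.24 | 68% | 75% |

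The T3 rows also assume a school slope variance of 0.02 and a within-child correlation of 0.5.

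**Step 4: arm-by-time.** This is the coefficient that, if significant, "would indicate the effect of the intervention depends on time". Under the same assumptions a constant region effect cancels from the T2-to-T3 change, and the SE is 0.0782 with or without region. The variance of a school's change is then 6 × 0.0782² = 0.0367. Suppose the regions also differ in that change:
- by 0.14: model variance 0.0367 + 36 × 0.0049/32 = 0.0422, SE √(0.0422/6) = 0.084; simulated type I 3.6%.
- by 0.24: 0.0367 + 0.0162 = 0.0529, SE 0.094; simulated type I 2.0%.

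The true SE stays at 0.078. A region main effect does not repair this; region-by-time does.

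**Step 5: child-level check.** A REML random-intercept fit (36 × 55, T1-T2 correlation 0.5, ICC 0.05 excluding region), with 0.3 outcome SD of region effect left after T1, gives model SE 0.112 against empirical 0.092 without region, and 0.091 against 0.092 with it. If T1 absorbs the whole regional difference, the model without region is correct (0.091 against 0.093).

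**Step 6: overlap of cohort and region** (child, gap 0.24). With 4 of 6 schools aligned, power is 81% against 87%; with 5 of 6, 83% against 87%; with 6 of 6 nothing is lost, because the cohort term already absorbs region.

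**The case against.** **Region is nowhere said to be prognostic.** A reader might infer it from the label of primary moderator, but modifying the treatment effect and predicting outcome are different properties. Only what remains after T1 counts. With T1-T2 correlation 0.5 the residual SD is √0.75 = 0.866, so a stable raw gap D leaves 0.5D/0.866 = 0.577D. A residual gap of 0.14 needs a raw difference of about 0.24 SD, and 0.24 needs about 0.42 SD. This stands: the loss is conditional.

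**The benchmark is a standardised mean difference, not a residual one.** This also stands. With correlation 0.5, raw 0.3 is 0.3/0.866 = 0.346 residual SD, and child T2 power at ICC 0.05 is 89% against 91% (gap 0.14) and 91% against 95% (gap 0.24). At raw 0.2 and gap 0.24 the loss is still about 10 points (56% against 66%).

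**The strata are not listed, and Figure 4, which is said to describe the Aim 1 model, is not in the text available.** Region as a stratum is therefore a reading, though two statements in the Protocol Summary and the matching list in section 4.4 all point to it. The prose and both equations agree that region is absent.

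**Region is in Aim 3.** That is a separate model and leaves the Aim 1 contrasts as they are.

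**Readings the documents do not support.** One is that the Aim 1 results would be biased or falsely significant; the error runs the other way. Another is that the arm-by-time test is safe in any case: nothing says that the region effect is constant from T2 to T3, and the longer-term model itself allows school slopes to vary. A third is that size and performance are omitted strata too; section 4.4 names them for matching, but no text says that allocation is made within them.

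**Conclusion.** The point holds as a conditional matter of efficiency. The plan appears to balance region by design and leaves it out of the Aim 1 models. If region predicts outcome after T1 score and cohort, the T2 and T3 level contrasts are conservative; if it also changes the trajectory, so is the arm-by-time test.

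The size cannot be fixed from the documents. Under the stated assumptions, with effect 0.3 and gap both in residual SD and ICC 0.05, the child T2 loss is 0, about 2 and about 7 points at gaps 0, 0.14 and 0.24. It is smaller at 0.3 if the effect is on the raw scale and T1 is predictive. If region is not prognostic, or if it coincides with cohort, nothing is lost on the level contrasts. The change should be made because it costs almost nothing and has to be fixed before outcomes are seen. The matched-pair label in section 6.1, which sits badly with three arms, is a separate wording point and adds no weight here.

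**What to change.** 1. Pre-specify urban/rural region as a fixed effect in the T2 and longer-term Aim 1 models, for child and teacher outcomes, and add region-by-time in the longer-term model.
2. State how the two cohorts fall across regions. If cohort and region coincide, the region term is neither estimable nor needed.
3. Confirm which factors define the randomisation strata, and treat any others in the same way.

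The cost is a few lines of SAP text and 1 df per term; region is known for every school. If region is not prognostic, going from 32 to 31 df at effect 0.3 and ICC 0.05 costs 0.08 power point for child outcomes (from about 78.4%) and 0.08 for teacher outcomes (from about 56.2%).

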**Figure 4. Aim 1 Effectiveness and Cost-Effectiveness Mechanisms**

**Data Analysis Plan for Aims 2.** For testing *PD/PDT* theory of change, Preacher's Multilevel Structural Equation Modeling (SEM) and MacKinnon's mediation model testing principles/strategies will be applied. Figure 5 below describes the model to be tested under Aim 2. Mediators (primary and secondary) will be examined separately. Only intermediate outcomes that show significant improvement will be examined in the mediation model testing. The mediation model will build on the effectiveness evaluation model (Aim 1 model), by including changing scores of mediators (T2-T1) and T2 to T3 child outcome trajectory because a mediation model is ideally tested in a design demonstrating time precedence in which the intervention occurs before the outcome. The mediation mechanism will be modeled as:  $Y_{ij} = \beta_1 I_j + \beta_2 t + \beta_3 I_j * t + \beta_4 M_j + \beta_5 C + \beta_6 X_{ij} + \gamma_j + \gamma_k + \epsilon_{ijk}$ .  $M_j$  is the value of the mediator at T2 and/or T3 for school  $j$ .  $\gamma_j$  and  $\gamma_k$  are the school- and class-level random effects. We will compare  $\beta_1$  and  $\beta_3$  from this model with the  $\beta_1$  and  $\beta_3$  from the effectiveness models that are not included the moderator ( $Y_{ij} = \beta_1 I_j + \beta_2 t + \beta_3 I_j * t + \beta_4 C + \beta_5 X_{ij} + \gamma_j + \gamma_k + \epsilon_{ijk}$ ). A significant effect of  $\beta_1$  and  $\beta_3$  in the mediation model will suggest a mediation effect. A conventional

[figure not shown]
Sober test described by Baron and Kenny will be applied next to test the significance of the mediation model. This modeling approach has been applied in our previous work. To confirm the model, Multilevel SEM will also be conducted (using Mplus).

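### The longer-term Aim 1 model names no T3 contrast that is reported whatever the interaction shows, and states no participant-level term for the paired T2 and T3 scores

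*Combined protocol and SAP*

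**What the plan says.** The Aim 1 plan in Section 9 commits to estimating impact after the intervention (T2) "and at one-year follow up (T3, 18 months after T1, or 12 months after T2"). It lists three comparisons: PD with control, PDT with control, and PD with PDT.

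T2 has its own model, adjusted for the T1 score and cohort. Its symbol key says that β1 "represents the intervention impact". On correlation, the plan says: "The model accounts for between-subject (within-school and -class) correlation by including school- and classroom-level (when appropriate) random intercepts".

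For T2 to T3 it moves to a growth curve: "The post-baseline scores will be modeled as a linear function of time/slopes, intervention indicator, and intervention-by-time interactions, adjusting for T1 scores and cohort". On random terms it says "we will add time-relevant parameters to the model above, including school-level random slopes". The printed equation has I, t, I×t, cohort, T1 score, a school effect, a class effect and ε. It does not show the school slope that the text promises. The residual, which "is the error term for student" i in school j and class k, carries no time index.

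The only follow-up step is conditional. If β3 (the I×t coefficient) is significant, then "in this case, we will estimate the slopes for each condition, and the difference between the conditions with respect to the mean outcome scores".

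The Aim 2 plan reuses this structure: "The mediation model will build on the effectiveness evaluation model (Aim 1 model), by including changing scores of mediators".

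**The concern.** There are two gaps in one model.

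**The T3 contrast.** The longer-term half of Aim 1 is a T3 comparison, but the model text does not say which quantity will be reported as the T3 effect. Time has no stated origin or unit. The only mean difference described depends on a significant β3 and names no time point. A benefit that is fully held from T2 to T3 has β3 = 0, so the result most favourable to the programme is the one for which the model text describes no comparison. The choice would then be made after the data are seen.

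**The participant term.** The same children and teachers are measured at T2 and T3. A model with school and class terms only treats a participant's two scores as independent, given school, class and T1 score. That ignores the pairing that makes a within-person change precise. The test affected is β3, the same test that opens the door to the mean comparison.

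**Working it through.** **1. What the fit can deliver.** There are two post-baseline waves, so a line in t with an arm-by-time term is a saturated mean model. The arm difference at time t is β1 + β3·t, and at T3 it is β1 + β3·t(T3). This value does not depend on how t is coded. The quantity is estimable; the plan does not name it.

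**2. What the literal rule does.** Take a benefit of 0.3 SD at both waves (the middle of the plan's 0.2 to 0.4 benchmark). Then β3 = 0, and a valid 5% test is significant about 5% of the time, less often if the test is conservative. The described mean comparison would be reached in no more than about one such trial in twenty. A direct T3 contrast would be informative: under the assumptions below with s = 0 its SE is 0.0917 (step 5), and 0.3/0.0917 = 3.27.

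**3. Inputs for the SE of β3.** From the documents: 12 schools per arm, about 55 children and about 15 teachers per school, T1 score in the model. The documents give no ICC or correlations, so these are assumed:
- total variance 1 and ICC 0.05, hence within-school variance 0.95;
- correlation 0.5 between the T1 score and each later score, at both levels;
- within-participant T2–T3 correlation r = 0.3, 0.5, 0.7;
- s, the variance of a school's T3-minus-T2 deviation, = 0, 0.01, 0.03;
- equal variances at both waves; class and cohort terms left out.

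**4. Formulas and results.** With n participants per school:
- True SE of β3 (t one unit apart) = √[4·0.95·(1−r)/(12n) + 2s/12]. The T1 score is equally correlated with both waves, so it cancels from the change.
- Smallest SE the model can report without a participant term = √[4·0.95·(1−0.5²)/(12n)]: 0.0657 for n = 55 and 0.1258 for n = 15.
- With the school slope in the model, fitted SE ≈ the larger of the two.

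Example, children, r = 0.7, s = 0: true SE = √(4·0.95·0.3/660) = 0.0416; ratio 0.0657/0.0416 = 1.58. At s = 0.01, true SE = √(0.001727 + 0.001667) = 0.0583; ratio 1.13.

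| Fitted/true SE of β3 | r = 0.3 | r = 0.5 | r = 0.7 |
|---|---|---|---|
| Children, s = 0 | 1.04 | 1.22 | 1.58 |
| Children, s = 0.01 | 1.00 | 1.00 | 1.13 |
| Children, s = 0.03 | 1.00 | 1.00 | 1.00 |
| Teachers, s = 0 | 1.04 | 1.22 | 1.58 |
| Teachers, s = 0.01 | 1.00 | 1.14 | 1.41 |
| Teachers, s = 0.03 | 1.00 | 1.01 | 1.18 |

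Simulation with the T1 covariate included gives, for children at s = 0, a type I error for β3 of about 3%, 1% and 0.1% against a nominal 5%.

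**5. The T3 contrast in the worst cell (s = 0, r = 0.7).** True variance = 2·0.75·(0.05 + 0.95/n)/12. The fitted variance adds a quarter of the excess in the variance of β3.
- Children: true 0.008409; excess (0.004318 − 0.001727)/4 = 0.000648; SE 0.0952 against 0.0917, ratio 1.04.
- Teachers: true 0.014167; excess (0.015833 − 0.006333)/4 = 0.002375; SE 0.1286 against 0.1190, ratio 1.08.

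**6. T3 timing.** The Endpoint row of the Protocol Summary has T3 12 months after T2. The text of Section 6.1 and Section 9 have it 12 months after T2 and about 18 months after T1. The note to the Table 1 timeline in Section 6.1 has it 6–7 months after T2, or 10–11 months after T1. The schedule therefore cannot supply the missing scale for t.

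**The case against.** Section 9 promises the T3 impact without condition and lists the three comparisons. The conditional sentence can fairly be read as an extra step for when the effect changes over time, not as a gate that cancels the promise. The T3 contrast is available from the stated fit. The phrase about T2 to T3 hints that T2 is the origin, and PROC MIXED could carry a repeated-measures covariance. All of this is fair, and it limits the point to specification. It does not answer it: no contrast, origin or participant-level covariance is written down.

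Two stronger readings are tempting and should not be drawn.

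- A reader might infer that β1 would be reported as the T3 effect, so that the answer would shift with the coding of t. The statement that β1 is the intervention impact belongs to the symbol key of the T2 equation. That key calls β2 the cohort effect and β3 the baseline effect, which does not fit the growth equation. Nothing says that the growth-model β1 will be presented as the T3 result. In Aim 2, the two models whose β1 values are compared would share one coding.
- A reader might compute the SE inflation without the T1 score and get larger ratios. The stated model contains that score, which absorbs part of the T2–T3 correlation, so those ratios do not describe it.

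**Conclusion.** The point stands as a should-fix on the text of the plan (Figure 4 is not reproduced in the available copy). The T3 effect is promised and estimable, but the model text names no T3 contrast, and its only mean difference is conditional on β3. That gap needs no assumption.

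The missing participant term makes the β3 test conservative, with a size that depends on unknown quantities. Under the stated assumptions the SE is overstated by up to 58% when school slopes do not vary. For children the overstatement is gone at s = 0.03; for teachers up to 18% remains there. The class and cohort terms were not modelled.

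It would be wrong to conclude that the T3 comparison is invalid. Its SE is at most 4% too large for children and 8% for teachers in the worst cell examined, in the conservative direction.

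**What to change.** - Define the longer-term effect as the model-based difference at T3, with 95% CI, for PD vs control, PDT vs control and PDT vs PD, reported whatever β3 shows.
- Treat wave as categorical, or set t = 0 at T3. Keep β3 as a secondary test of fade-out or growth.
- Add a participant random intercept or an unstructured T2–T3 residual covariance within participant, and carry the same structure into the Aim 2 mediation model.
- Write the promised school random slope into the printed equation.
- Reconcile the T3 timing in the Table 1 timeline note with the Protocol Summary, the text of Section 6.1 and Section 9.

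The cost is SAP wording and a few lines of PROC MIXED code; no new data are needed.
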